- The Suicidality SOP instructs the use of the C-SSRS and uses the responses to questions 4 and 5 as a threshold for physician involvement. If the responses to these two questions are “yes” then the study physician will be contacted for in-person assessment or for phone call-back assessment as appropriate. The C-SSRS will be completed while awaiting the physician.
- The following mood rating items and thresholds trigger use of the Suicidality SOP: C-SSRS, “yes” to questions 4 and 5; MINI, “yes” on items B7, B9 or B10; MADRS, 4 or 6 on item 10; BDI, 2 or 3 on item 9.

We note that the CGI is used for withdrawal criteria, but this scale is not used for suicidality assessment, but rather to ensure safe continuation of the study.

b. Medication or Therapy Changes

At the phone screen and on site screening, potential subjects are informed that we do not ask them to discontinue their medications or treatments. However, we ask that they do not make changes to their medications or therapy prior to or during the experimental study period. Stable medication is not a confound. Subjects are also told that if their clinician believes it is in their best interest to make this change, they should do so. They will be asked to inform us if this is the case. We will not ask the subject to withdraw from the study, but their data will be excluded from analyses. If a subject withdraws from the study due to a change in medication, pregnancy or any other reason not related to the actual LFMS procedures and would like to return to the study in the future, they will be allowed to re-enroll. However, they must go through a 2 month washout period. The subject will be partially rescreened to confirm mood state and inclusion/exclusion criteria prior to their first treatment visit.

c. Study visits and parameters to be measured (e.g., laboratory tests, x-rays, and other testing)

Measures

Screening measures

- M.I.N.I International Neuro-Psychiatric Interview (MINI)
- Cumulative Illness Rating Scale – Geriatrics (CIRS-G)
- Montgomery Asberg Depression Rating Scale (MADRS)
- Mini Mental State Exam (MMSE)
- Hamilton Anxiety Rating Scale (HARS)
- Positive and Negative Affect Schedule-Extended (PANAS-X)

Low Field Magnetic Stimulation: Initial Trial in Geriatric Bipolar Depression

- LFMS Medical Screening Form
- LFMS Medications Form
- Clinical Global Impressions – Baseline (CGI-B)

Safety Measures

- Columbia Suicide Severity Rating Scale (C-SSRS)

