For safety purposes, use of the LFMS device follows standard MRI procedures. The LFMS device is assessed by the McLean Hospital Biomedical Engineering department annually to ensure the device operates within safe parameters.

e. Withdrawal Criteria:

Participation in this research study is voluntary. Subjects will be informed that they may withdraw from this study at any time. Subjects also will be informed that study staff may terminate participation at any time if they feel that it is in the best interest of the subject or study.

Objective criteria for removing a subject from the study include: if they become no longer eligible for the study between screening and treatment per inclusion/exclusion criteria (e.g. drug use or pregnancy), if they have dangerous or active suicidal ideation at any time during the study (as determined by C-SSRS and suicide related questions on the MADRS and the opinion of a study clinician), or if their CGI-I score, determined as part of the Safety Measures, shows a change of ≥ 8 , or if any intolerable discomfort from the study procedures occurs.

f. Source of subjects and recruitment methods

Study subjects will be recruited via clinician referrals from the Geriatric Psychiatry Mood and Anxiety Disorders Outpatient Clinic (GPMADOC) and the SAGE Program, located in South Belknap. Clinicians associated with these

Low Field Magnetic Stimulation: Initial Trial in Geriatric Bipolar Depression

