Clinical Global Impressions-Improvement Scale (CGI-I)			X	X	X	X	X	X	X	X
Clinical Global Impressions-Baseline		X								
Adverse Events Check-in		X	X	X	X	X	X	X	X	X

*Administered twice per visit, immediately before and immediately after LFMS treatment.

Safety Procedures

h. Suicidality Procedures

Suicidal ideation (SI) is not uncommon in people suffering from GBD. Suicidality will be assessed throughout the study during the screening visit, treatment visits and follow-up visits. Using the C-SSRS. The GPMADOC suicidality SOP will be prompted by over threshold responses for certain items on mood rating scales or by spontaneous report of suicidal ideation at any time. Specifically,

- The use of the GPMADOC Suicidality SOP will be triggered by spontaneous report of suicidal ideation or by over-threshold responses to specific items on mood ratings.
- The Suicidality SOP instructs the use of the C-SSRS and uses the responses to questions 4 and 5 as a threshold for physician involvement. If the responses to these two questions are “yes” then the study physician will be contacted for in-person assessment or for phone call-back assessment as appropriate. The C-SSRS will be completed while awaiting the physician.
- The following mood rating items and thresholds trigger use of the Suicidality SOP: C-SSRS, “yes” to questions 4 and 5; MINI, “yes” on items B7, B9 or B10; MADRS, 4 or 6 on item 10.

We note that the CGI is used for withdrawal criteria, but this scale is not used for suicidality assessment, but rather to ensure safe continuation of the study.

i. Medication or Therapy Changes

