The Safety Measures will be administered. As part of these, the C-SSRS will be used as a suicidality risk assessment and any positive response to items 4 or 5 will prompt the use of the Suicidality SOP (see ‘Suicidality Procedures’ above). The second part of the Safety Measures is the CGI-I, which will be used to ensure safe continuation of the study; a score of 6 or more will prompt a consultation with the study physician and potential withdrawal from the study (see “Withdrawal Criteria” above). Medication and/or treatment changes will be asked about and noted. Changes in treatment will not prompt withdrawal but will indicate that data will be excluded from analysis (see “Medication and Therapy Change Procedures” above). A brief progress note will be recorded. The Short- and Long-Term mood scales will be

Low Field Magnetic Stimulation: Initial Trial in Geriatric Bipolar Depression

administered, and LFMS procedures will begin immediately after these mood ratings are completed. HARS and MADRS Long-Term mood scales will only be administered on Visits 3, 5, and 7.

Randomization occurs automatically when the subject number is entered on the LFMS Device during the first treatment visit.

For LFMS procedures, the subject will lie down on the patient table with his/her head positioned inside the device cylinder, and the operator will start the LFMS device. The device has been designed so that the cylinder does not extend below the eyes in order to reduce claustrophobia. Subjects will be instructed to remain silent during the treatment, except in cases of discomfort, desire to discontinue treatment, or similar situations related to subject safety and study participation. Subjects will be given one 20 minute exposure to either the LFMS or sham electromagnetic field treatment. Subjects will be told they may receive either the active treatment or a sham, inactive treatment.

After treatment, the Short-Term Measures will be completed again to obtain post-treatment scores. Subjects will also be asked about possible side effects or sensations. After the treatment and mood ratings, subjects may leave immediately or rest in the Imaging Center waiting area until they are ready to leave or return to the GPMADOC and the SAGE Program, located in South Belknap.

Follow-up Visit (Visit 8)

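### The MADRS item 10 trigger for the Suicidality SOP lists two non-adjacent scores, which fits the over-threshold rule only if no score between them can be recorded

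*Combined protocol and SAP*

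**What the plan says.** The general rule is in section V of the combined protocol and SAP, under Suicidality Procedures (item a in Phase 1, item h in Phase 2). In both phases the SOP is "triggered by spontaneous report of suicidal ideation or by over-threshold responses to specific items on mood ratings".

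The specific list is introduced with the words "The following mood rating items and thresholds trigger use of the Suicidality SOP". In Phase 1 its last two entries read "MADRS, 4 or 6 on item 10; BDI, 2 or 3 on item 9". In Phase 2 the BDI is no longer used and the list ends with "MADRS, 4 or 6 on item 10". The MADRS entry is the same in both phases, so it is not a stray fault in one copy of the text.

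Other provisions bear on the same risk:

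- **C-SSRS.** The LFMS visit procedures in both phases say that "any positive response to items 4 or 5 will prompt the use of the Suicidality SOP". The visit tables schedule this scale at every visit and, in Phase 2, at both follow-up calls.
- **Withdrawal Criteria, Phase 2 (section III.e).** Dangerous or active suicidal ideation is judged "as determined by C-SSRS and suicide related questions on the MADRS and the opinion of a study clinician", with no numeric cut-off for the MADRS item.
- **Psychosocial risks (section VII).** Increased suicidal thinking, including when it comes to light in conversation with staff, leads to an immediate call to a study physician and the subject's own clinician.

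**The concern.** A threshold rule cannot switch off as the score rises. Once a score is high enough to trigger, every higher score triggers too. A list of two values with a gap between them breaks that property if a score inside the gap can be recorded. A rater who follows the list as written would then open the SOP at the lower listed score and not at the more severe one above it.

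Item 10 also carries more weight in Phase 2 than in Phase 1. The BDI trigger has gone, and the MINI, whose items are also on the list, is given only at screening. After screening, MADRS item 10 is the only listed rating-item trigger apart from the C-SSRS. A safety rule should not depend on each rater working out what the list was meant to say.

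**Working it through.** No sample size, power or error rate is involved, and no score frequencies are given. The check is a comparison of texts.

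**Step 1: what the over-threshold wording implies.** Write the rule as: trigger if score ≥ t, for some cut-off t. A score of 4 is listed as a trigger, so t ≤ 4. Then 5 > 4 ≥ t, so 5 must trigger as well. The same holds if the rule is written with a strict inequality.

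**Step 2: what the list says.** Read literally, the trigger set is {4, 6}, and 5 is not in it.

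**Step 3: where the two differ.** They can differ at 5, and only if 5 can be recorded. Two cases follow, taking 6 as the highest possible score (also an assumption, since the documents do not give the range):

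| Recordable scores from 4 upward | Over-threshold rule met by 4 | Literal list | Conflict |
|---|---|---|---|
| 4, 5, 6 | 4, 5, 6 | 4, 6 | yes, at 5 |
| 4, 6 (even scores only) | 4, 6 | 4, 6 | none |

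The documents do not say which case applies. They neither give the scoring steps nor say that the entry means 4 and above.

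**Step 4: the BDI comparison.** The Phase 1 BDI entry lists 2 and 3, which are adjacent, so it has no gap. This shows that the MADRS entry is the odd one out. It does not show which case in the table is true, because both entries could simply be lists of the response options printed on a form.

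**Step 5: what else would catch the subject.** In the Phase 2 visit table, MADRS is rated at Visits 1, 2, 3, 5, 7 and 8 and at both calls. The C-SSRS is scheduled at every one of these contacts. The Suicidality Procedures also say that the SOP's own step is to administer the C-SSRS, and that its questions 4 and 5 decide whether a physician is involved. On the steps the documents describe, missing the MADRS trigger therefore means missing a route to a scale already scheduled at that contact.

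**Step 6: limits of that backstop.** There are two.

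- The Phase 2 LFMS visit procedures describe the C-SSRS before the mood scales, with stimulation directly after the latter. If that order is followed, item 10 can be the later of the two checks before exposure.
- The C-SSRS condition itself is worded in two ways. The trigger list joins questions 4 and 5 with *and*; the visit procedures join them with *or*. That is a separate inconsistency, but it means the backstop is not cleanly specified either.

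**The case against.** The strongest reply is that the fault depends on a fact outside the documents. If the study's form offers only even values for item 10, the entry is a complete list of the options from 4 upward and agrees with the over-threshold wording. That stands, and it is why the point is conditional.

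The second reply is that little follows even if a 5 can be recorded. The C-SSRS is scheduled at the same contact, spontaneous report opens the SOP at any time, the withdrawal criteria use the MADRS suicide questions and clinician opinion without a number, and the described SOP leads back to the C-SSRS. This largely stands too. The full SOP is not in the documents, so no further consequence of a missed MADRS trigger can be claimed.

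A reader might infer that a subject with an intermediate score would escape the safety procedure altogether. The documents do not support that: only the MADRS route would fail. A reader might also take the number of scheduled MADRS ratings as the size of the problem. It is not. The relevant count is ratings scored between the two listed values with no other route triggered, and nothing in the documents allows that to be estimated.

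What survives is that the plan describes one safety trigger in two ways and does not supply the fact that would make them agree.

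**Conclusion.** The concern holds as a minor correction. In both phases the general rule is a threshold, while the MADRS item 10 entry is two non-adjacent values. The two agree only if no score between those values can be recorded, and the plan does not say so. If such a score can be recorded, a literal reading leaves it off the MADRS trigger although a lower score is on it.

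The size cannot be stated. The frequency is unknown and may be zero, and the effect is limited to one of several routes to the SOP. The conclusion rests on one open assumption, the scoring steps on the study's form. It implies no view on which score ought to trigger the SOP.

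**What to change.** Reconcile the item 10 entry with the over-threshold wording in the Suicidality Procedures of both phases, and make the rating checklist match. Either express the entry so that every recordable score is plainly on or off the trigger, or keep the two values and add a clause saying that only even scores are recorded. The clinical team decides where the trigger starts; no cut-off is suggested here. The *and*/*or* wording of the C-SSRS condition should be reconciled in the same edit, since the same list carries both.

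The cost is one phrase in each phase and one line on the checklist. The design, visit schedule and analysis are not affected.

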This study will consist of a screening visit; three treatment visits (3 days active or sham LFMS) and one follow-up visit for ratings one week after initial treatment. This is followed one week later by 3 visits with the alternate treatment (3 days active or sham LFMS) and a follow up visit for ratings one week later.

Visits & Procedures	Screening Week 1	LFMS experimental treatment Week 2			Follow-Up Visit Week 3	LFMS experimental treatment Week 4			Follow-Up Visit Week 5
	Visit 1	Visit 2	Visit 3	Visit 4	Visit 5	Visit 6	Visit 7	Visit 8	Visit 9
LFMS		X	X	X		X	X	X	
M.I.N.I International Neuro-Psychiatric Interview (MINI)	X								
Cumulative Illness Rating Scale (CIRS-G)	X								
Mini Mental State Exam (MMSE)	X								
LFMS Demographics Form	X								
LFMS Medical Screening Form	X								
LFMS Medications Form	X								
Drug Test	X								
Montgomery-Asberg Rating Scale (MADRS)	X	X			X	X			X
Hamilton Anxiety Rating Scale (HARS)	X	X			X	X			X
Positive and Negative Affect Schedule-Extended (PANAS-X)	X	X	X	X	X	X	X	X	X
Beck Anxiety Inventory (BAI)		X	X	X		X	X	X	
Beck Depression Inventory (BDI)		X	X	X		X	X	X	
Columbia Suicide Severity Rating Scale (C-SSRS)	X	X	X	X	X	X	X	X	X

Low Field Magnetic Stimulation: Initial Trial in Geriatric Bipolar Depression

Clinical Global Impressions – Improvement Scale (CGI-I)		X	X	X	X	X	X	X	X
Clinical Global Impressions – Baseline (CGI-B)	X								
Adverse Events Check-in	X	X	X	X	X	X	X	X	X

Safety Procedures

a. Suicidality Procedures

Suicidal ideation (SI) is not uncommon in people suffering from GBD. Suicidality will be assessed throughout the study during the screening visit, treatment visits and follow-up visits. Using the C-SSRS. The GPMADOC suicidality SOP will be prompted by over threshold responses for certain items on mood rating scales or by spontaneous report of suicidal ideation at any time. Specifically,

- The use of the GPMADOC Suicidality SOP will be triggered by spontaneous report of suicidal ideation or by over-threshold responses to specific items on mood ratings.

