At the phone screen and on site screening, potential subjects are informed that we do not ask them to discontinue their medications or treatments. However, we ask that they do not make changes to their medications or therapy prior to or during the experimental study period. Stable medication is not a confound. Subjects are also told that if their clinician believes it is in their best interest to make this change, they should do so. They will be asked to inform us if this is the case. We will not ask the subject to withdraw from the study, but their data will be excluded from analyses. If a subject withdraws from the study due to a change in medication, pregnancy or any other reason not related to the actual LFMS procedures and would like to return to the study in the future, they will be allowed to re-enroll. However, they must go through a 2 month washout period. The subject will be partially rescreened to confirm mood state and inclusion/exclusion criteria prior to their first treatment visit.

j. Study visits and parameters to be measured (e.g., laboratory tests, x-rays, and other testing)

Measures

Screening measures

- M.I.N.I International Neuro-Psychiatric Interview (MINI)
- Cumulative Illness Rating Scale – Geriatrics (CIRS-G)

Low Field Magnetic Stimulation: Initial Trial in Geriatric Bipolar Depression

- Montgomery Asberg Depression Rating Scale (MADRS)
- Mini Mental State Exam (MMSE)
- Hamilton Anxiety Rating Scale (HARS)
- Positive and Negative Affect Schedule (PANAS)
- LFMS Medical Screening Form
- LFMS Medications Form
- Clinical Global Impressions – Baseline (CGI-B)

Safety Measures

- Columbia Suicide Severity Rating Scale (C-SSRS)
- Clinical Global Impressions – Improvement Scale (CGI-I)

Long-term measures

- Montgomery-Åsberg Depression Rating Scale (MADRS)
- Hamilton Anxiety Rating Scale (HARS)
- Repeatable Battery for the Assessment of Neuropsychological Status (RBANS)
- Young Mania Rating Scale (YMRS)

Short-term measures

- Positive and Negative Affect Schedule (PANAS)

Screening (Visit 1) Procedures

A study staff member will obtain informed consent (see consent procedures above IV.b.). If informed consent is obtained, then the screening procedures will proceed.

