The Monday following the set of 5 treatments (visits 3-7), subjects will meet with the study staff for a non-treatment follow-up visit. This visit will last up to 1 hour. During this visit, the Safety measures will be administered. As part of these, the C-SSRS will be used as a suicidality risk assessment and any positive response to items 4 or 5 will prompt the use of the Suicidality SOP (see ‘Suicidality Procedures’ above). Medication and/or treatment changes will be asked about and noted. Changes in treatment will not prompt withdrawal but will indicate that data will be excluded from analysis (see “Medication and Therapy Change Procedures” above).

The Long-term measures will be completed, as well as the PANAS. Subjects will be asked if they have experienced any change in their mood or noticed any effects. In addition, subjects will be asked whether they think they received active or sham LFMS.

Follow-up Phone Calls

In order to determine whether any effects are still felt after treatment stops, study staff will make one follow-up phone call each week on Monday for the 2 weeks after the Follow-up Visit. Short- and Long-Term Measures will be administered, and study staff will ask whether the subject has experienced any adverse side-effects. Safety Measures including the C-SSRS and the CGI-I will be administered, and a positive response to question 4 or 5 on the C-SSRS will trigger the Suicidality SOP.

k. Drugs to be used (dose, method, schedule of administration, dose modifications, toxicities), include Toxicity Grading Scale (if applicable)

N/A

l. Devices to be used

The LFMS Device is an electromagnetic coil situated on a cylinder with an inside diameter of 13.2 inches. It produces weak electromagnetic fields at a frequency of about 1000Hz; the magnetic fields are less than 30 Gauss and the electric fields are up to 1.43 V/m. A fully detailed description of the electromagnetic field distribution and waveform has been presented in the IDE submission to the FDA (and determined to be a non-significant risk device).

m. Procedures/surgical interventions, etc.

N/A

n. Data to be collected and when the data is to be collected

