During the treatment visits, research data will be obtained through mood rating scales before and after the LFMS procedures, and through self-report from the subjects. Research data will also be obtained from subjects through mood rating scales at the follow-up visits, one week after the start of the set of 5 experimental LFMS procedures.

VI. BIOSTATISTICAL ANALYSIS

d. Specific data variables being collected for the study (e.g., data collection sheets).

The primary long-term measures will be the change in MADRS and HARS scores at one week compared to baseline across the treatment week. This analysis will be a repeated measures ANOVA with a baseline covariate. The primary short-term analyses using the PANAS scores, which provide additional insight into the details of mood change, will be performed in the same way.

e. Study endpoints

The main endpoint of this study is that participants will well tolerate 5 daily active treatments. A secondary endpoint is the expectation that participants will experience a persistent increase in positive mood at one week after the start of treatment. Change in mood over the first treatment is an additional measure that will ensure comparability of the study to previous studies.

f. Statistical methods and Power analysis

This is an exploratory study being performed to characterize the effects of LFMS over daily treatments and at one week in a target population. As the endpoints are safety and tolerance by the participants, no power analysis has been performed. We expect to be able to make the first estimate of an effect size based on the results of this study.

VII. RISKS AND DISCOMFORTS (Stratify by common and uncommon)

d. Complications of surgical and non-surgical procedures, etc.

Risks Related to Confidentiality and Privacy

There is a risk that a breach of privacy or confidentiality could occur. But, all study staff are trained in how to preserve confidentiality and privacy. Risks will be minimized by storing subject data and personal information on a password protected computer or in a locked filing cabinet in a locked office, accessible only to study staff.

Psychosocial (non-medical) risks

There is a risk that questions during the treatment visits about mental health and mood state may upset the subject psychologically. Subjects are free to take a break from or to stop answering these questions at any time, and a study physician will be able to assist them if needed.

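### Subjects whose medication or therapy changes after randomisation are dropped from the analyses, which can bias the active–sham mood comparison and leaves the tolerability set unclear

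*Combined protocol and SAP*

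**What the plan says.** Phase 2, section V, Medication or Therapy Changes, asks subjects to keep medication and therapy constant but allows for clinical need: "Subjects are also told that if their clinician believes it is in their best interest to make this change, they should do so". The consequence for the data follows: "We will not ask the subject to withdraw from the study, but their data will be excluded from analyses". The Phase 2 procedures for Visits 3–7 and for Visit 8 repeat it: "Changes in treatment will not prompt withdrawal but will indicate that data will be excluded from analysis". Phase 1 has the same rule in its own Medication or Therapy Changes section and in the procedures for its treatment and follow-up visits.

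Allocation is made when the subject number is entered on the device at the first treatment visit (section IV and the LFMS Procedures, both phases).

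Section VI of Phase 2 names the change in MADRS and HARS at one week as the primary long-term measures, analysed by repeated measures ANOVA with a baseline covariate, with PANAS handled the same way. On the purpose it says: "We expect to be able to make the first estimate of an effect size based on the results of this study". On the endpoint: "The main endpoint of this study is that participants will well tolerate 5 daily active treatments". Section VI of either phase defines no analysis population, missing-data method or sensitivity analysis.

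A subject who withdraws for a reason unrelated to the LFMS procedures, such as a medication change, and who "would like to return to the study in the future, they will be allowed to re-enroll", after a two-month washout.

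**The concern.** A change first made after the first treatment visit removes a subject who has already been allocated. The change is made on the clinician's judgement of the subject's interest. In people enrolled with a MADRS of at least 20, worsening or unimproved mood is a plausible reason for it. Exclusion can then depend on the outcome being compared, and the remaining groups are no longer the randomised groups. Blinding does not prevent this when the treatment works, because a real effect alters mood and so alters who is excluded. The effect-size estimate is what is at stake.

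Three further points are unclear rather than shown to be wrong:

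- **Tolerability.** The word for analyses carries no qualifier, so the rule could be read to remove treated subjects from the main endpoint.
- **Extent.** It is not said whether all of a subject's ratings go, or only those after the change. Phase 1 is a crossover ("This is followed one week later by 3 visits with the alternate treatment"), so a change in the second period could delete a complete first period. In Phase 2, "study staff will make one follow-up phone call each week on Monday for the 2 weeks after the Follow-up Visit"; a change in those weeks could delete a one-week rating already taken.
- **Re-enrolment.** It is not said how a returning subject is allocated or which course is analysed.

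**Working it through.** There is no figure in the plan to reproduce: it gives no power calculation, SD or expected rate of medication change. The numbers below are illustrations.

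**Inputs from the documents.** Phase 2: 1:1 allocation and 32 completers, so 32/2 = 16 per arm; randomisation on the Monday of treatment and the one-week rating the next Monday, about 7 days. Phase 1: 10 completers; Visit 2 (week 2) to Visit 9 (week 5), about 3 weeks.

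**Assumptions.** MADRS change is normal with SD 6, 8 or 10; sham mean −4; true benefit 0, 3 or 5 points; only non-improvers (change above 0) change treatment, each with probability p.

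**Formula, Phase 2.** With q = P(X > 0) and m = E[X | X > 0], the retained mean is (μ − p·q·m)/(1 − p·q).

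**Worked case (SD 8, benefit 5, p = 0.50 in both arms).**

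- Sham, μ = −4: q = 0.3085, m = 5.129, excluded p·q = 15.4%. Retained mean = (−4 − 0.1543 × 5.129)/0.8457 = −5.665.
- Active, μ = −9: q = 0.1303, m = 4.009, excluded p·q = 6.5%. Retained mean = (−9 − 0.0651 × 4.009)/0.9349 = −9.907.
- Estimated benefit = 9.907 − 5.665 = 4.24 points instead of 5.0, an attenuation of about 15%.

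**Whole grid, Phase 2.**

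| Situation | Result |
|---|---|
| Benefit 3 or 5, p 5–10% in both arms | understated by 1.0–2.5% |
| Benefit 3 or 5, p 25–75% in both arms | understated by 5.9–28.8% |
| No effect, equal p | bias 0 |
| No effect, p 10% sham, 25% active | false benefit 0.32–0.63 points |
| No effect, p 25% sham, 50% active | false benefit 0.59–1.22 points |
| No effect, p 50% sham, 25% active | false harm 0.59–1.22 points |

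**A second model**, in SD units with 16 per arm and no true effect: if exclusions of the worst-scoring subjects differ by 2 between arms (2 against 0, or 4 against 2), the spurious difference is about 0.18–0.22 SD and the two-sided 5% type I error rises to about 10.5–12.7%.

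**Phase 1 crossover**, by simulation, dropping the whole subject for a change in either period, p 25–75%: attenuation about 3–18% with a between-period correlation of 0.5, and about 6–29% with correlation 0. With SD 8, benefit 5, p = 0.50 and correlation 0.5, 5.0 points becomes about 4.57 and 19.9% of subjects are excluded, so 10 completers leave 10 × 0.801 ≈ 8.

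**Tolerability.** If the rule applies there, one excluded active subject is 1/16 = 6.25% of the completers in that arm.

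**The case against.** The strongest reply is that few changes are likely. Medication must be stable for two weeks before screening, subjects are asked not to change, and the Phase 2 window to the one-week rating is about 7 days. Half of all non-improvers changing in that time is a severe assumption; at 5–10% the loss is at most 2.5%, or about 0.1 point on 5. This stands, and the worked case should not be read as an expected value.

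The model also triggers exclusion on the final score, whereas a change made before the rating can respond only to earlier mood. Triggering on an earlier score with the same mean and SD reduces the attenuation in the worked case from about 15% to about 10.6%, 7.6% or 4.5% for assumed correlations of 0.7, 0.5 and 0.3. That is correct; the bias shrinks but does not vanish.

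Unequal rates by arm are hard to motivate under blinding with no true effect. That is fair, so the false-benefit rows show what is possible rather than what is likely. Whether ratings after a change belong in the main analysis is a choice of estimand, and the illustrations do not quantify the effect of including them.

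On tolerability, adverse events are checked, recorded and reported, and nothing says they are dropped; if all 64 permitted subjects were treated, one exclusion would be 1/32 ≈ 3% of an arm. The phone-call section does not mention asking about medication changes, so that route is uncertain. The study calls itself exploratory, which lowers the urgency, but it still names primary mood measures and promises an effect size.

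**Conclusion.** The concern holds. The rule is stated consistently in both phases, it acts after randomisation, its trigger can depend on outcome, and nothing in the statistical section repairs it. Following the plan as written can therefore bias the active–sham estimates for MADRS and HARS, and for the short-term scales analysed in the same way (PANAS in Phase 2). Changes made before the first treatment visit do no such harm.

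The existence of the problem is certain; its size is not. It depends on an unstated rate of change and on the assumed SD, means and trigger, and it could be negligible in Phase 2. In groups this small, though, one or two exclusions can matter. The effect on tolerability, the extent of deletion and the handling of re-enrolled subjects are gaps in wording, not demonstrated errors. This should be fixed.

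**What to change.** Replace the exclusion rule in both phases with text such as:

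> All randomised subjects are analysed in their assigned arm (or sequence) using all ratings collected, regardless of medication or therapy change. Everyone who received at least one LFMS session is in the tolerability analysis. An analysis excluding ratings after a change is a sensitivity analysis. Counts, timing and reasons for changes are reported by arm.

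Two additions would complete it. First, subjects who withdraw contribute ratings up to withdrawal, with a named missing-data method (a likelihood-based mixed model for repeated measures is one option). Second, for re-enrolled subjects, state that the first randomised course enters the primary analysis and how a returning subject is allocated.

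The cost is low: protocol wording and a short definition of analysis sets. Subjects who change treatment remain in the study, so their ratings are already scheduled. The main estimate will then include any effect of the concomitant change, a small drawback that the sensitivity analysis addresses. Nothing here alters when a clinician may change treatment.
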